Section 1: Administrative information:

1.1 Purpose of SAP

The purpose of SAP is to provide the details of procedural methods used including inclusion, exclusion, the kind of patient enrolment, the flow of study, stopping rule and analysis used as part of the COPLA-II trial for publication.

1.2 Trial and Trial registration

Efficacy of Convalescent Plasma Therapy in Patients With COVID-19

Trial registered with ClinicalTrial.gov (identifier: NCT04425915).

1.3 SAP Version: First version written on 10th June 2020. With sample 400 (200 in each group)

1.4 Protocol Version: First version written on 10th June 2020.

1.5 SAP revisions: No

1.6 Roles and responsibility:

1.6.1.1 [name] [name]: Chief Coordinator/Clinical Lead

1.6.1.2 [name]: Chief investigator/principal investigator

1.6.1.3 [name]: Senior Statistician

1.6.1.4 [name]: Clinical Trial Coordinator.

1.6.1.5 [name]: Wrote the SAP

SECTION 2

INTRODUCTION:

2.1 Background and rationale:

The outbreak of SARS-CoV2 infection, which had originated in Wuhan, China, has become a pandemic involving more than 10 million people across the globe with almost half million deaths and still counting (1). The case-fatality rate of COVID-19 has ranged from 1.2-13% (1,

2). The current evidence-based strategy relies on providing supportive care in mild to moderate cases and providing mechanical ventilation and extracorporeal membrane oxygenation in severe cases. There is no targeted drug therapy available at present. Some studies have indicated benefits with, intravenous Remdesivir and Dexamethasone in reducing the duration and severity of illness, but not mortality (3-5). Apart from antiviral drugs, virus-specific neutralizing antibodies, which could accelerate virus clearance and prevent entry into target cells, could serve as a mechanism for the restriction and clearance of the viruses by the host. The plasma of convalescent patients who have recovered from SARS-CoV2 infection may contain such neutralizing antibodies which may accelerate virus clearance in an infected recipient and be used in the treatment of patients with COVID-19 (6). The experience of using convalescent plasma is derived from its utility in improving the survival rate of patients with SARS infection wherein the patients who had no response to intravenous corticosteroids showed improvement. Providing passive antibody therapy by convalescent plasma in COVID-19 infection could be one of the approaches towards disease mitigation in the absence of definitive treatment (5, 6). This approach can be effective in patients before they develop a humoral response to COVID-19.

2.2 Objectives:

2.2.1 Primary objective:

Efficacy of convalescent plasma in severe COVID 19 patients in time to clinical improvement (Clinical improvement: Reduction of two points in ordinal scale or live discharge from the intensive care unit, whichever is earlier) [Time Frame: Day 28]

The six-point scale is as follows:

- a. death=6;
- b. hospital admission for extracorporeal membrane oxygenation or mechanical ventilation=5;

- c. hospital admission for non-invasive ventilation or high-flow oxygen therapy=4;
- d. hospital admission for oxygen therapy (but not requiring high-flow or non-invasive ventilation) =3;
- e. hospital admission but not requiring oxygen therapy=2;
- f. discharged or having reached discharge criteria (defined as clinical recovery-ie, normalization of pyrexia, respiratory rate 94% on room air, and relief of cough, all maintained for at least 72 h) =1.

2.2.2 Secondary objectives:

1. Proportion of patients in each category according to the ordinal scale
[Time Frame: 48 hours]
2. Proportion of patients in each category according to the ordinal scale [Time Frame: 7 day]
3. Proportion of patients in each category according to the ordinal scale
[Time Frame: Day 14]
4. Proportion of patients in each category according to the ordinal scale
[Time Frame: Day 28]
5. Duration of oxygen therapy in both groups [Time Frame: Day 28]
6. Duration of hospital stay in both groups [Time Frame: Day 28]
7. Proportion of patients on mechanical ventilation at day 7 in both groups
[Time Frame: Day 7]
8. Mortality in both groups [Time Frame: Day 7]
9. Mortality in both groups [Time Frame: Day 28]

10. Duration of Intensive Care Unit stay [Time Frame: Day 28]
11. Incidence of adverse effects in both groups [Time Frame: Day 28]
12. Presence of antibodies against SARS-CoV-2 in serum after plasma administration
[Time Frame: Day 0] (IgG Titres against S1, RBD antigen, and SARS CoV2
neutralizing antibody titres)
13. Presence of antibodies against SARS-CoV-2 in serum after plasma administration
[Time Frame: Day 7] (IgG Titres against S1, RBD antigen, and SARS CoV2
neutralizing antibody titres)
14. Change in Cytokines in both groups
15. Change in acute phase reactants in both groups

Section 3: Study Methods

3.1 Trial design: It will be a open-labeled; phase III randomized controlled trial.

3.2 Randomization: The randomization will be done by using stratified block randomization method into two treatment groups. The allocation concealment will be done by using “Sequentially Numbered Opaque Sealed Envelopes” (SNOSE) method.

3.3 Sample size: The sample size was calculated by assuming median survival in SMT as 24 days, and convalescent plasma with 18 days giving a reduction of 25% of the median time; then with $\alpha=5\%$ and $\beta=20\%$, we need to enrol 190 participants in each treatment arm by survival analysis method. $(Z_{1-\alpha/2}+z_{\beta})^2/((\ln(\theta))^2)$ where $Z_{1-\alpha/2}=1.96$ and $z_{\beta}=0.84$, $\theta=\lambda_1=\log 2/24$ $\lambda_0=\log 2/18$. Hence, we enrolled 400 cases which were equally and randomly allocated into two arms

3.3 Framework: it will be a comparative trial with the motive of testing the efficacy of convalescent plasma in severe COVID 19 patients with standard medical trial.

3.4 Treatment allocation:

Patients will be randomized to one of two groups by block randomization:

- **Group A:** Convalescent Plasma plus standard medical treatment
- **Group B:** Standard medical treatment only.

3.5 Statistical interim analysis and stopping guidance:

3.5.1 Statistical interim analysis:

Since it is of short duration trial no interim analysis is proposed.

3.5.2 Stopping guidance: No stopping rule is proposed until or unless ethical or IRB or designated government authority may ask for stopping the trial.

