5.3 Recruitment: Consort flow will include as per protocol-

Patients will be assessed for eligibility >>>randomization will be done for eligible participants >>> Allocation of treatment in two groups (one arm will be given convalescent plasma with standard medical treatment and another arm will be given standard medical treatment only) >>> follow up till 28 days.

5.4 Withdrawal/ Follow-up: Withdrawal is not expected, follow up till 28 days in all enrolled patient.

5.5 Baseline patient characteristics: following variables will be considered:

- Age at screening (years) = date of screening.
- Time from initial admission to randomization(days) = date of transfusion allotment by snooze method and transfusion of plasma.
- O₂ saturation at baseline.
- PiO₂/FiO₂ ratio at baseline.
- Respiratory rate at baseline.
- Need of Mechanical ventilation at baseline.
- SOFA score at baseline.
- For those who died: Date of death – transfusion start date or date of randomization.
- For those who are alive: Date of last follow-up – transfusion start date or date of randomization.

Section 6:

Analysis

6.1 Outcome definitions:

6.1.1 Definition of primary endpoint: Time to clinical improvement (Clinical improvement: Reduction of two points in ordinal scale or live discharge from the intensive care unit, whichever is earlier)

6.1.2 Secondary endpoints:

1. The proportion of patients in each category according to the ordinal scale at 48 hours and day 7, 14, and 28 after randomization
2. Duration of oxygen therapy
3. Duration of hospital stay
4. The proportion of patients on mechanical ventilation at day 7. (after randomization)
5. Mortality at day 7 and day 28 (after randomization)
6. Duration of Intensive Care Unit stay
7. Incidence of adverse effects in both groups
8. Presence of antibodies against SARS-CoV-2 in serum after plasma administration.
9. Cytokines and acute phase reactants

6.2 Analysis methods:

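### The 190 per arm is a count of events, not patients: under the plan's own assumptions, 400 patients followed for 28 days give about 61% power, not 80%

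*SAP*

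**What the plan says.** SAP section 3.3 (Sample size) bases the calculation on "assuming median survival in SMT as 24 days, and convalescent plasma with 18 days giving a reduction of 25% of the median time". It takes two-sided 5% significance (z = 1.96), β = 20% (z = 0.84) and exponential hazards equal to log 2 divided by each median. It concludes that "we need to enrol 190 participants in each treatment arm by survival analysis method" and ends: "Hence, we enrolled 400 cases which were equally and randomly allocated into two arms". The formula contains only the two z-values and ln θ. It has no term for length of follow-up, censoring or the probability of an event.

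The primary endpoint (sections 2.2.1 and 6.1.1) is time to clinical improvement, and section 2.2.1 sets its time frame at Day 28. Section 5.4 sets follow-up for everyone: "Withdrawal is not expected, follow up till 28 days in all enrolled patient". The log-rank test is the comparison named for time-to-event data (sections 3.5.4 and 6.2). No interim analysis is planned (section 3.5.1).

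**The concern.** A formula built only from z-values and the log hazard ratio gives the number of events that a log-rank test needs. To turn events into patients, one divides by the probability that a patient has the event during follow-up. Section 3.3 omits that step and presents the event count as the number to enrol.

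The omission matters because the follow-up window is short compared with the assumed medians. By the definition of a median, half the controls are still unimproved at day 24, and observation ends at day 28. Many patients will be censored, so the trial will have far fewer events than the formula requires.

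This is the only power statement for the primary endpoint of a phase III trial. If the result is null, readers will judge it against 80% power. With no interim look or sample-size review, nothing later in the plan would bring the discrepancy to light.

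**Working it through.** **Inputs, all from the SAP.** Medians 24 and 18 days, exponential times, z = 1.96 and 0.84, 190 per arm calculated and 200 per arm enrolled (section 3.3); 28 days of follow-up and no withdrawals (section 5.4); log-rank test (section 3.5.4).

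**1. Reproducing the 190.**
- The hazard ratio is 24/18 = 1.333, and ln(1.333) = 0.28768.
- The formula as printed gives (1.96 + 0.84)² / 0.28768² = 7.84 / 0.08276 = 94.7.
- With a factor of 2: 2 × 94.73 = 189.5, which rounds up to the stated 190 per arm.
- With a factor of 4: 4 × 94.73 = 378.9. This is the standard total number of log-rank events under 1:1 allocation.

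So 190 per arm is half of the required 379 events. The arithmetic is right for events; the label is wrong.

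**2. Events expected by Day 28.** For exponential times, P(improved by day 28) = 1 − 2^(−28/median).
- Standard treatment: 1 − 2^(−28/24) = 0.5546.
- Plasma: 1 − 2^(−28/18) = 0.6598.
- With 200 per arm: 200 × (0.5546 + 0.6598) = 242.9 events.
- With 190 per arm: 190 × 1.2144 = 230.7 events.

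**3. Power.** Power = Φ(ln HR × √(events)/2 − 1.96).

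| Design | Events | Power |
|---|---|---|
| Required by the formula | 379 | 80% |
| All 400 patients improve | 400 | 82% |
| 200 per arm, 28 days | 243 | 61.1% |
| 190 per arm, 28 days | 231 | 58.9% |

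For 200 per arm: 0.28768 × √242.9 / 2 − 1.96 = 2.242 − 1.96 = 0.282, and Φ(0.282) = 0.611.

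**4. Checks by other methods.** A log-rank simulation with censoring at day 28 (10,000 runs, 200 per arm) gives 61.1%. An exponential rate-difference formula with fixed 28-day follow-up gives 60.7%.

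**5. What would restore 80%.**
- *Larger effect, same 400 patients.* Medians of 24 versus 16.8 days (hazard ratio 24/16.8 = 1.43) give 200 × (0.5546 + 0.6850) = 247.9 events. Power is then Φ(0.3567 × √247.9 / 2 − 1.96) = 80%.
- *Same effect, more patients.* The mean event probability is (0.5546 + 0.6598)/2 = 0.607. For 380 events, 380 / 0.607 is about 626 patients, or 313 per arm.

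**The case against.** **The 61% depends on the shape of the curve.** This is the strongest objection. With Weibull times that keep the medians at 24 and 18 days, power for 400 patients is 42% at shape 0.8, 78% at 1.2, 80% at about 1.23 and 94% at 1.5. The dependence is real, so the 61% should always be quoted with its model. But section 3.3 itself sets the hazards at log 2 over the median, which is the exponential model. The shapes that reach 80% do so mainly through a larger hazard ratio: at shape 1.2 it is 1.333^1.2 = 1.41, not the 1.333 behind the 190. They do not support the calculation as written.

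**Deaths.** Patients who die unimproved might be thought to lower power further. If the stated medians ignore death, they do: assumed constant death hazards of 0.005 to 0.02 per day in both arms give about 9% to 31% deaths on standard treatment by Day 28, and power of 59% to 52%. If the medians already count deaths as not improved, that loss is included in the 243 events. The SAP does not say which applies, so this is a conditional remark and not part of the 61%.

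**Wording and typography.** Calling a time to improvement a survival time is common shorthand, and the missing factor 2 and the garbled definition of θ may come from reading the PDF. Neither carries the finding.

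**It is only a disclosure.** The correction changes no test or estimate, and section 4.1 promises 95% confidence intervals, which would show the imprecision. That is fair, but the stated β would still be wrong for the primary endpoint.

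**Conclusion.** The sample-size statement is wrong as written. The 190 per arm is a number of events, and nothing in the SAP converts it into patients, although follow-up ends at Day 28. Under the plan's own assumptions (exponential times, medians of 24 and 18 days, two-sided 5%, no withdrawals), 400 patients yield about 243 of the 379 events required. Power is about 61% and the type II error about 39%, against the stated 80% and 20%. The 20 patients added above the calculated 380 raise power only from 59% to 61%. Even a one-sided test, which the z-value of 1.96 at 1 − α/2 rules out, would reach only 72%. The exact figure moves with the assumed distribution, but the stated method does not support 80%.

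**What to change.** Keep 400 patients and rewrite section 3.3 so that it:

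- gives the formula as 2(z₁₋α/2 + z_β)² / (ln θ)², with θ the ratio of the two hazards, and states that it yields 190 **events** per arm, 379 in total;
- gives the expected proportions improved by Day 28 (55.5% and 66.0%) and the resulting 243 or so events from 400 patients;
- states power of about 61% for 24 versus 18 days, and 80% for about 24 versus 16.8 days, both under exponential times;
- names the quantity as median time to clinical improvement, and says whether the medians count patients who die as not improved.

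The cost is SAP wording and a less favourable stated power; no patients, visits or analyses are added. Section 3.3 describes enrolment in the past tense while other sections use the future. If recruitment was still open, the sponsor should also know that 80% power for 24 versus 18 days would need about 626 patients. If it was closed, the change is a disclosure that lets a null result be read correctly.

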3.5.3 Details of guidelines for stopping the trial early: Nil

3.5.4 Statistical analysis:

Continuous variables will be expressed as mean (SD) or median (range) and compared by Student's t-test or Mann-Whitney U test as appropriate. The categorical data will be analyzed using Chi-Square or Fisher's exact test. To compare pre and post values, a paired t-test or Wilcoxon signed-rank test will be used. To find out the predictor in survival analysis Cox-proportional hazard regression analysis will be applied. The actuarial probability of survival will be calculated by the Kaplan-Meier graph and compared by the log-rank test. The p value < 0.05 will be considered statistically significant.

3.5.5 Timing of final analysis: The final trial analysis will be performed once the trial is completed or the recruitment of patients ends or at the end of follow up (probably Jan 2021)

3.5.6 Timing of outcome assessments: Jan 2021.

Section 4: Statistical Principals:

4.1 Confidence intervals and P-values: The p value < 0.05 will be considered statistically significant.

Description and rationale for any adjustment for multiplicity:

No adjustments to the type I error will be made as there will be two groups.

Confidence intervals to be reported: Will be reported at 95%.

4.2 Adherence and Protocol deviations: No protocol deviation is expected and will adhere to the defined protocol of trial.

4.3 Analysis populations:

4.3.1 Definition of analysis populations:

Intention-to-treat (ITT) analysis of the sample/population of interest will be carried out in the severe COVID-19 infected individuals. There is no plan to do per-protocol (PP) population analysis as none will be allowed to switch to other treatment group.

4.3.2 ITT population:

This population includes all patients that will be randomized regardless of treatment adherence.

All summaries and analysis will be on the ITT population unless otherwise specified.

4.3.3 PP population:

Not applicable.

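### SAP 3.5.5 allows the final analysis to be triggered by the end of recruitment, up to 28 days before the last recruits complete Day 28

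*SAP*

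**What the plan says.** Section 3.5.5 of the SAP times the final analysis "once the trial is completed or the recruitment of patients ends or at the end of follow up", with a tentative date in brackets ("probably Jan 2021"). It does not say whether the earliest or the latest of these events governs. It does not require the last patient to reach Day 28, or the database to be locked, first.

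Other sections fix a 28-day horizon for each patient:

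- Section 2.2.1 gives the primary endpoint, time to clinical improvement, a Day 28 time frame.
- Section 5.3 ends the patient flow at 28 days, and section 5.4 states "follow up till 28 days in all enrolled patient".
- Sections 2.2.2 and 6.1.2 list mortality and ordinal-scale categories at Day 28. Section 2.2.2 also sets a Day 28 time frame for the durations of oxygen therapy, hospital stay and ICU stay.

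Sections 3.5.4 and 6.2 assign chi-square or Fisher's exact tests to categorical data, t or Mann-Whitney tests to continuous data, and Kaplan-Meier, log-rank and Cox methods to time-to-event data. Section 4.3.2 puts every randomised patient in the ITT population. Section 6.3 expects no missing data and names no imputation method. On interim looks, section 3.5.1 says: "Since it is of short duration trial no interim analysis is proposed".

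**The concern.** A patient randomised on the last day of recruitment has no Day 28 outcome on that day. An analysis run then follows the letter of 3.5.5 but not 5.3 and 5.4.

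The cost would differ by endpoint. Mortality and ordinal category at Day 28 would be missing for late recruits who are still alive, and their durations of oxygen therapy, ICU stay and hospital stay could be cut short. The tests planned for these endpoints take each value as complete. Late recruits cannot simply be left out, because the ITT population includes them, and no imputation rule exists to fall back on. The primary endpoint would lose events and therefore power.

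The wording also leaves the analysis date open in an open-label trial (section 3.1).

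**Working it through.** **Inputs from SAP section 3.3 (sample size):** median 24 days on standard treatment and 18 days on plasma, ratio 0.75; two-sided alpha 5% (1.96) and beta 20% (0.84); 400 patients, equally allocated. **Assumptions, not in the SAP:** exponential event times, no competing deaths, and uniform accrual over R days, with R = 150 to 230.

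**1. The plan's own figure.** (1.96 + 0.84)² = 7.84 and (ln 0.75)² = 0.08276. Per arm, 2 × 7.84 / 0.08276 = 189.5, rounded up to 190. The stated 190 per arm is reproduced, as a count of events (380 in total).

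**2. Analysis after everyone reaches Day 28.**
- Hazards: ln 2/24 = 0.02888 and ln 2/18 = 0.03851 per day.
- P(event by Day 28) = 1 − exp(−28λ) = 0.555 and 0.660.
- Expected events: 200 × (0.5546 + 0.6598) = 243.
- Power = Φ(√243/2 × |ln 0.75| − 1.96) = Φ(2.242 − 1.96) = 61%.

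The gap between 61% and the planned 80% arises because 380 is an event count and only about 61% of 400 patients are expected to have an event by Day 28. That is a separate matter; here 61% is only the reference value.

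**3. Analysis on the day recruitment ends.** Patients enrolled in the last 28 days have follow-up spread evenly from 0 to 28 days.
- Number with less than 28 days: 400 × 28/R = 74.7 (18.7%) at R = 150 and 48.7 (12.2%) at R = 230.
- Their average event probability is 1 − (1 − exp(−28λ))/(28λ) = 0.314 and 0.388, against 0.555 and 0.660 with full follow-up. The loss per late recruit, averaged over arms, is (0.240 + 0.272)/2 = 0.256 events.

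| | Full follow-up | R = 150 | R = 230 |
|---|---|---|---|
| Patients with < 28 days | 0 | 75 | 49 |
| Expected events | 243 | 224 | 230 |
| Events lost | – | 74.7 × 0.256 = 19 | 48.7 × 0.256 = 12 |
| Power | 61% | 57.6% | 58.8% |

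Faster accrual is worse: at R = 90 days, 124 patients are incomplete, 211 events are expected and power is 55%.

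**4. Type I error if both dates were tested.** The two log-rank statistics have correlation √(information fraction). The fractions are 224/243 = 0.92 and 230/243 = 0.95. The chance that at least one exceeds 1.96 in absolute value under no effect is 6.3% and 6.1%. A single analysis, at a date not chosen on results, keeps 5%.

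**The case against.** The strongest reply is that 3.5.5 is loose rather than wrong. The SAP states 28-day follow-up repeatedly, and 3.5.5 itself mentions the end of follow-up. Read as a whole, the plan intends complete follow-up; the early cut is permitted, not planned. That stands, and it limits the weight of the point. It does not remove the point, because nothing in 3.5.5 says that the later event governs.

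Further parts of the reply also stand:

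- Completion of the trial and end of follow-up may well be the same milestone. One phrase is at fault, not three competing triggers.
- Kaplan-Meier and log-rank methods accommodate administrative censoring. The primary comparison would not be biased by the early cut, and the power loss is 2 to 4 points.
- The 49 to 75 patients are an upper bound. A late recruit who has died already has a known Day 28 mortality outcome and ordinal category, and one who has already improved has a complete primary outcome.

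A reader might infer that the wording amounts to an unplanned second look, or that the date would be picked once results are visible. The SAP does not support this. It describes one final analysis, plans no interim look and ties recruitment to a fixed 400 patients. Open label means that individual allocation is known; it does not show that comparative results have been computed. The 6% figure needs a test at both dates and a claim on either.

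A reader might also fault section 3.5.6 for giving a month ("Timing of outcome assessments: Jan 2021") instead of assessment days. Those days stand in 2.2.2 and 6.1.2, so this is editorial and no part of the point.

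**Conclusion.** The point holds in a narrow form. Section 3.5.5 permits a final analysis up to 28 days before the last recruits have the follow-up that 5.3 and 5.4 require. The main harm is to the Day 28 and 28-day secondary endpoints: at most about 49 to 75 of 400 patients would be incomplete, and the planned tests and section 6.3 offer no defined way to deal with them. For the primary endpoint the harm is modest: 12 to 19 of 243 expected events, and power of 58-59% in place of 61%.

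That the end of recruitment precedes Day 28 for the last recruits follows from the SAP text alone. The sizes rest on exponential times with the SAP's medians and on the assumed accrual of 150 to 230 days, so they are indicative. Inflation of type I error is conditional on behaviour that the SAP does not describe and is not part of the conclusion.

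**What to change.** In section 3.5.5, delete the end-of-recruitment alternative and state one trigger, for example: the final analysis is performed after the last randomised patient has died or completed Day 28 and the database has been locked. The expected calendar month can stay as information only.

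The cost is one sentence of SAP text and a wait of at most 28 days after the last enrolment. No change to sample size, endpoints or tests is needed for this point.
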